### 3.5 FOLLOW-UP

All persons will be followed for SAEs for 14 days after last application of topical ruxolitinib. All participants, including those who discontinue therapy for any reason, will receive a follow-up phone call 6 weeks (+/- 4 weeks) after discontinuation of topical ruxolitinib (week 12). The phone call will focus on a) survival status and cause of death if applicable, b) ongoing topical and/or systemic treatment for cGVHD and date of discontinuation, c) primary malignancy progression, d) any second primary malignancy, e) return to work part-time or full-time. Primary and contributing causes of death are to be recorded in the CRF and the patient's medical record.

### 3.6 STUDY CALENDAR

**Table 2: Study Calendar**

Procedure	Screen	Baseline	Week 2	Week 4	Week 6	Follow-up Week 12
Visit window	(D-28 to -1)		± 3 bus. days		± 3 bus. days	+ 4 weeks
Informed consent	X					

**Abbreviated Title:** Topical ruxolitinib in cGVHD**Version Date:** 01/25/2021

Procedure	Screen	Baseline	Week 2	Week 4	Week 6	Follow-up Week 12
Visit window	(D-28 to -1)		+ 3 bus days		+ 3 bus days	+ 4 weeks
Ruxolitinib and placebo cream BID		X	X	X		
History and PE	X	X	X	*	X	
Vital signs	X	X	X	*	X	
Karnofsky or Lansky performance Score	X	X	X		X	
PGA score		X	X	*	X	
cGVHD diagnosis assessment (2014 NIH Criteria)		X			X	
Labs:						
CBC + differential	X	X	X	*	X	
BUN + Creatinine	X	X	X	*	X	
Hepatic Panel	X	X	X	*	X	
Serum b-hCG 	X	X	X	*	X	
HIV 1/2 antibody	X					
HBsAg	X					
Anti-HCV antibody	X					
CMV and EBV PCR	X	X	X	*		
Surface area measures		X	X	*	X	
Clinical photography		X	X	*	X	
Skin biopsies	X				*	
Total body photography		*	*	*	*	
Correlative Research Studies		X			X	
Pharmacokinetics			X			
Response Evaluation: Overall disease severity VAS, Pruritus VAS, Pain VAS		X	X	*	X	
Adverse Events			X	X	X	X
Concomitant Medications	X	X	X	X	X	X
Study drug dispensation/return/accountability		X	X	*	X	

\*Optional

**Abbreviated Title:** Topical ruxolitinib in cGVHD

**Version Date:** 01/25/2021

Only in women of childbearing potential age. Exceptions include women status-post hysterectomy or in menopause > 1 year since last menstrual period.

### **3.7 SURGICAL GUIDELINES**

A skin biopsy will be obtained during screening (may be performed at an outside facility) to confirm epidermal cGVHD. At week 6, skin biopsies will be obtained from the 2 treated sites at the investigator's discretion. Skin biopsy procedure will be explained to the patient and informed consent will be obtained.

The risk of infection, scarring, nerve damage, pigment change, numbness, bleeding, pain, and allergy to anesthesia will be reviewed. The biopsy site will be locally anesthetized. Size of punch biopsies will be up to 6mm. One punch biopsy will be performed from each of the 2 treatment sites. Sutures will be placed for hemostasis. Petrolatum and bandage will be applied to the wound site and wound care will be reviewed. Written wound care instructions will be given. We will instruct the patient regarding suture removal.

### **3.8 CRITERIA FOR REMOVAL FROM PROTOCOL THERAPY AND OFF STUDY CRITERIA**

#### **3.8.1 Criteria for removal from protocol therapy**

- Completion of 6-week protocol therapy
- Progressive disease in skin or other organ system requiring an increase or change in systemic therapy
- Participant requests to be withdrawn from active therapy
- Unacceptable toxicity as defined in Section 11.1.2
- Investigator discretion
- Pregnancy

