### **3 STUDY IMPLEMENTATION**

#### **3.1 STUDY DESIGN**

This is a phase II, placebo controlled study to evaluate the safety, tolerability, and efficacy of 1.5% topical ruxolitinib cream, INCB018424, in patients with epidermal cGVHD. Case series and anecdotal reports of systemic JAK inhibitors in cGVHD have suggested a benefit for cGVHD involvement of the skin and other organs, warranting further study. For patients with cGVHD that manifests with primarily epidermal skin disease, effective topical therapy is desirable. Current topical therapies (corticosteroids and calcineurin inhibitors), can have significant side effects and are not specific to the disease pathology.

In this study, patients with a minimum of 2 distinct areas of involvement with intact (no ulceration) epidermal cGVHD that has been confirmed histologically, will be eligible for participation. Each participant will receive active study agent and placebo. Chronic GVHD is a heterogeneous disease with a waxing and waning course. Given the heterogeneity and the natural history of this disease as well as use of concurrent systemic medications, each participant will serve as his/her own control to allow for better comparison of placebo and active study drug. Randomization table generated by [name], statistician, will be provided to the pharmacy, such that the labeling of placebo and active study drug as container A and B will be randomized at the pharmacy. All participants will be provided with active study drug to apply to the designated affected area (maximum application BSA of 10%) twice a day and a second container containing a vehicle cream to be applied twice a day on a second affected area. Subjects who experience dose limiting toxicities (DLT) will have the dose adjusted as described in Section 3.1.1.

**Abbreviated Title:** Topical ruxolitinib in cGVHD

**Version Date:** 01/25/2021

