### 3.1.1 Dose Limiting Toxicity

DLT will be defined as any grade  $\geq 3$  adverse event which is thought to be probably or definitely related to the investigational drug. Grade 3 toxicities that resolve within 72 hours to  $\leq$  grade 1 with supportive care (e.g. pruritus, nausea, vomiting, fatigue, diarrhea) will not be counted as DLTs. Study drug and placebo will be held until resolution of any grade  $\geq 3$  adverse event. If 2 subjects experience a grade 3 AE probably or definitely attributable to the study drug, the study will be stopped for safety review. In patients that have experienced disease progression, further dosing will cease in a patient at the occurrence of the first DLT. All patients will be evaluable for toxicity from the time of their first treatment with topical ruxolitinib until the end of study participation, regardless of inclusion in primary response evaluation.

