### 3.3 DOSE MODIFICATIONS

**Table 1: Dose Modifications**

All dose modifications will be discussed with the PI or MAI.

Adverse event	CTCAE grade/attribution	Protocol Action
Any adverse event (excluding ulceration, infection, treatment-related malignancy)	Grade 2 >7 days that is probably or definitely related to study drug.	Hold study drug; *If AE resolves to ≤ grade 1 or baseline within 7 days: resume dose. ** If AE does not resolve to ≤ grade 1 or baseline within 7 days: patient comes off drug.
Any adverse event (excluding ulceration, infection, treatment-related malignancy)	Same grade 2 >7 days recurs that is probably or definitely related to study drug.	Hold study drug; *If AE resolves to ≤ grade 1 or baseline within 7 days: decrease dose to once daily. **If AE does not resolve to ≤ grade 1 or baseline within 7 days: patient comes off drug.
Any adverse event (excluding ulceration, infection, treatment-related malignancy)	Same grade 2 >7 days recurs after dose reduction that is probably or definitely related to study drug.	Patient comes off drug.
Any adverse event (excluding ulceration,	Grade 3 that is probably or definitely related to study drug.	Hold study drug; *If AE resolves to ≤ grade 1 or baseline within 7 days:

**Abbreviated Title:** Topical ruxolitinib in cGVHD

**Version Date:** 01/25/2021

infection, treatment-related malignancy)		decrease dose to once daily. **If AE does not resolve to $\leq$ grade 1 or baseline within 7 days: patient comes off drug.
Any adverse event (excluding ulceration, infection, treatment-related malignancy)	Same grade 3 recurs after dose reduction that is probably or definitely related to study drug.	Patient comes off drug.
Any adverse event (excluding ulceration, infection, treatment-related malignancy)	Grade 4 that is probably or definitely related to study drug.	Patient comes off drug.
Skin ulceration at treatment site	Any grade	Patient comes off drug.
Infection	Grade 2 that is probably or definitely related to study drug.	Hold study drug until completion of systemic antibiotic course and resolution of infection, then restart at same dose level.
Infection	Grade 2 recurs that is probably or definitely related to study drug.	Hold study drug until completion of systemic antibiotic course and resolution of infection, then decrease dose to once daily.
Infection	Grade 2 recurs after dose reduction that is probably or definitely related to study drug.	Patient comes off drug.

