#### **Evaluation of Benefits and Risks/Discomforts**

##### **10.3.1 Related to topical ruxolitinib**

Subjects participating in this research protocol may benefit from an improvement in symptoms of cGVHD. Potential risks of topical ruxolitinib include the toxicities described in Section 11.1.2 and in the consent form. There is the potential for unexpected adverse events. All subjects will be monitored for development of side effects.

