### 11.1.2 Toxicity

Topical ruxolitinib has been evaluated in over 2350 subjects in at least 17 clinical studies in healthy volunteers and participants with psoriasis, atopic dermatitis, alopecia areata and vitiligo for a duration of 1-26 months.

There have been no treatment related deaths. To date, only one severe, and/or life-threatening treatment emergent adverse event (TEAE), dermatitis atopic, has been attributed to the study drug. All other SAEs were considered unlikely related or unrelated to study drug.

Other TEAEs that led to discontinuation of topical ruxolitinib include mild to moderate occurrences of application site irritation, a Grade 3 elevation in GGT, headache, fatigue, nausea, atopic dermatitis and hypertriglyceridemia.

In an ongoing study of atopic dermatitis, a total of 67 pediatric participants (aged 2 to 17 years) received ruxolitinib cream 0.5%, 1.5%, or 0.75% cream BID. No participant had a fatal TEAE, SAE, or TEAE leading to discontinuation of ruxolitinib cream.

Cutaneous AEs were seen with similar frequency for vehicle-treated lesions and active comparator treated lesions when compared with topical ruxolitinib treated lesions.

The most common AEs that were considered possibly related to the study drug include transient hypoesthesia, transient leukopenia and reticulocytosis, pruritus, upper respiratory infections, nasopharyngitis, headache, acne, dermatitis atopic, and transient application site irritation. All were considered mild to moderate and resolved with or without the need for concomitant medications.

Oral ruxolitinib is FDA approved for treatment of myelofibrosis and polycythemia vera in adults. The most common AEs with oral administration include thrombocytopenia, anemia, neutropenia, infection, nonmelanoma skin cancer, elevation of AST and ALT. Systemic exposure with topical ruxolitinib is several fold below the doses that are associated with AEs following oral dosing.

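### The toxicity criterion for removal in 3.8.1 has no definition behind it, the DLT pointer in 3.1 leads to a section without the reduction steps, and 3.1.1 and Table 1 disagree

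*Combined protocol and SAP*

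**What the plan says.** Section 3.8.1 lists the grounds for removal from protocol therapy. The toxicity ground reads "Unacceptable toxicity as defined in Section 11.1.2". The list also includes progression that requires a change of systemic therapy, and the investigator's discretion. It cites neither Section 3.1.1 nor Table 1.

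Section 11.1.2 reports prior experience with the product. It opens with exposure ("Topical ruxolitinib has been evaluated in over 2350 subjects in at least 17 clinical studies"), moves to events that ended treatment in those studies ("Other TEAEs that led to discontinuation of topical ruxolitinib include mild to moderate occurrences of application site irritation"), and says of the common possibly related events that "All were considered mild to moderate and resolved with or without the need for concomitant medications". Phototoxicity and genotoxicity paragraphs follow.

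Section 3.1 states: "Subjects who experience dose limiting toxicities (DLT) will have the dose adjusted as described in Section 3.1.1". Section 3.1.1 defines a DLT and gives three actions: a hold, a study-level stop for safety review, and an end to dosing at the first DLT in patients who have progressed. The stepwise rules for hold, reduction to once daily and removal are in Table 1 of Section 3.3, with rows such as "Same grade 3 recurs after dose reduction that is probably or definitely related to study drug".

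**The concern.** These are the rules that decide when a patient stops or interrupts the creams. A reader who follows 3.8.1 to its stated source finds no threshold. A reader who follows 3.1 to its stated source finds actions, but not the reduction that dose adjustment would lead one to expect, and those actions differ from the ones in Table 1. So the route taken through the protocol can change what is done for the same event.

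Safety and tolerability are a primary objective. Dosing also decides who is analysed: Section 8.3 restricts the analysis set to patients who receive at least 80% of scheduled doses.

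**Working it through.** The plan gives no figure to reproduce on this point, so the check is textual.

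**Reference 1: 3.8.1 to 11.1.2.** Section 11.1.2 contains exposure counts, earlier discontinuations, common events and a comparison with oral use. It gives no grade, duration or attribution rule for this trial and does not define unacceptable toxicity. Section 10.3.1 uses the same section as background: "Potential risks of topical ruxolitinib include the toxicities described in Section 11.1.2 and in the consent form". The text is present and is not redacted. The definition is absent.

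**Reference 2: 3.1 to 3.1.1.** Section 3.1.1 has dosing actions but no reduction step. Reduction to once daily appears only in Table 1.

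**Section 3.1.1 against Table 1.** The hold sentence in 3.1.1 begins "Study drug and placebo will be held until resolution of any grade" and goes on to cover grade 3 or higher events.

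| Point | 3.1.1 | Table 1 |
|---|---|---|
| Attribution | Hold for any grade 3 or higher event, related or not | Generally a probable or definite relation; treatment-site ulceration, grade 4 infection and treatment-related malignancy are worded differently |
| Product | Study drug and placebo | Study drug only |
| Time | Until resolution, no limit | For general events, 7 days to reach grade 1 or lower, or baseline; otherwise off drug |
| Related grade 4 event | Hold until resolution | Off drug |
| Related grade 3 event settling to grade 1 or lower within 72 hours with supportive care | Not a DLT | No exemption; hold, then once daily |
| Grade 3 DLT after progression | Dosing ends | Once daily if it settles within 7 days |

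The last two rows describe general events, that is, not ulceration, infection or treatment-related malignancy.

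**Illustration of how this can reach the analysis set.** Twice daily for 6 weeks is 2 × 7 × 6 = 84 applications. The 80% requirement is 0.80 × 84 = 67.2, so at least 68 must be given and at most 16 (8 full days) may be missed. Assume an unrelated grade 3 event, not ulceration, infection or malignancy, that lasts 10 days, and assume that withheld doses count as scheduled.

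- Under 3.1.1, 20 doses are withheld: 64/84 = 76.2%, and the patient falls outside the set.
- Under Table 1, no row applies, so there is no hold and the patient can stay in.

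The 10 days and the treatment of withheld doses are assumptions; the plan states neither. With a hold of 8 days or less and no other missed doses, the patient stays in under either section.

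**The case against.** The strongest reply is that removal still works in practice. Table 1 states its off-drug outcomes in its own right and does not need 3.8.1. The investigator's discretion in 3.8.1 gives any such removal a route. Section 3.3 requires every dose modification to be discussed with the principal or medical advisory investigator, and Section 7.7.1 has the team discuss each patient every two weeks. The documents describe one research team, so divergence between sites is not a realistic picture. Grade 1 events are not collected (Section 6.1.1), so removal for trivial events is unlikely.

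All of this stands and limits the consequence. It does not supply the missing definition: a criterion that says it is defined elsewhere promises a fixed rule, and discretion puts judgement in its place. Nor does it settle which of 3.1.1 and Table 1 the team should follow.

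Two differences are narrower than they look. Section 4.2 uses study drugs in the plural for both creams, and under the blind a hold of the active cream alone would be hard to carry out, so Table 1 may mean both. Progression that requires a change of systemic therapy already leads to removal under 3.8.1, so the cessation rule matters only for other progression.

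A reader might infer that 3.8.1 and Table 1 pick out different patients, for example because 11.1.2 does not mention ulceration. The documents do not support this. The criterion in 3.8.1 has no content to compare, so selection under it is indeterminate, not different. A reader might also infer that 3.1.1 gives no dosing instruction at all; it gives a hold and a cessation rule and lacks only the reduction step.

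**Conclusion.** The point holds as an inconsistency in operative rules that should be corrected. One reference (3.8.1 to 11.1.2) leads to no definition, one (3.1 to 3.1.1) leads to a section without the reduction steps, and 3.1.1 and Table 1 differ on six points. Attribution, the time limit and related grade 4 events are the clearest of these.

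Its effect on the results cannot be sized. The plan gives no expected rate of grade 3 or higher events. One patient's share of a planned 10 evaluable patients would show only that patient's weight, not a bias. The illustration shows that the conflict can change membership of the analysis set, not that it will. The conclusion rests on the text as printed and implies nothing about which clinical rule is right.

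**What to change.** Correct the references in 3.8.1 and 3.1 so that each leads to a section that contains the rule it promises. Reconcile 3.1, 3.1.1, 3.3 (Table 1), 3.8.1 and 11.1.2 so that one consistent rule set governs hold, reduction and removal. That rule set should state attribution, which creams are affected, any time limit, the handling of grade 4 events and of grade 3 events that settle quickly, and what applies after progression. The sponsor decides which of its existing rules applies; none is proposed here.

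The cost is a short text amendment: two references and the reconciled wording. Sample size and test are unchanged. Whether any working instruction changes depends on the rules the sponsor keeps.

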#### **3.8.2 Off-Study Criteria**

- Completion of study follow-up period
- Participant requests to be withdrawn from study
- Death

## **4 CONCOMITANT MEDICATIONS/MEASURES**

All prescription and nonprescription medications, including topical agents, used during the study period will be recorded on the appropriate pages of the CRF. Patients will be advised to contact the study team prior to initiating any new medication.

### **4.1 CONCOMITANT CORTICOSTEROID THERAPY**

Participants may remain on systemic corticosteroids during the course of the 6-week study at a stable or tapering dose. If a pulse of corticosteroids is required for cutaneous or other organ cGVHD, the patient will be withdrawn from the study. Topical corticosteroids may not be used for the duration of this study.

**Abbreviated Title:** Topical ruxolitinib in cGVHD

**Version Date:** 01/25/2021

#### **4.2 OTHER TREATMENTS FOR cGVHD**

- Other systemic treatments such as calcineurin inhibitors (tacrolimus or cyclosporine), sirolimus, mycophenolate mofetil, or other immunosuppressants must be maintained at a stable or tapering dose. Dose adjustments based on drug interactions or maintaining therapeutic drug level will be permitted.
- Patients cannot initiate new immunosuppressant or immunomodulatory therapeutic interventions, including extracorporeal photopheresis or phototherapy, during the 6 weeks of the study.
- Patients cannot apply topical medications, prescription or nonprescription, besides the study drugs for the duration of this study. All topical therapies, except emollients, should be discontinued at least 1 week prior to start of therapy.

### **5 BIOSPECIMEN COLLECTION**

#### **5.1 CORRELATIVE STUDIES FOR RESEARCH/PHARMACOKINETIC STUDIES**

##### **5.1.1 Skin biopsy**

A skin biopsy will be obtained during screening and 2 skin biopsies will be obtained at week 6, at the discretion of the investigator, one from each of the 2 treatment sites. Skin biopsies will be bisected and a section will be sent to the Laboratory of Pathology in formalin for histologic assessment with hematoxylin and eosin stain. Unstained slides will be made for immunohistochemical studies to evaluate the T-cell infiltrates, IFN-induced transcription markers, pSTAT, and myofibroblast and pericyte markers. The additional tissue will either be placed in OCT and processed, stored, and analyzed at the ETIB pre-clinical core and/or in [name]’s lab or will be immediately processed for single cell RNA sequencing (gene expression and lymphocyte receptor sequencing) in the Dermatology Branch.

##### **5.1.2 Immunologic assays from blood**

Peripheral blood will be obtained for immunologic assays. Heparinized plasma will be assayed for BAFF, CXCL9, CXCL10, IL-6, TNFa, and other IFN-induced chemokines. Whole blood will be collected for flow cytometry of lymphocyte populations. Changes in CD3, CD4, CD8, B cells, and NK cells will be assessed at baseline compared to week 6 in the Clinical Center’s CLIA certified immunophenotyping lab. Additional assessments of regulatory, naïve, memory and effector T cells will be performed in the ETIB Preclinical Core lab. Single cell RNA sequencing, including lymphocyte receptor sequencing, may be done from peripheral blood in the Dermatology Branch.

##### **5.1.3 Measurement of ruxolitinib serum levels**

Blood samples for the determination of plasma levels of ruxolitinib will be obtained from each patient via 6mL sodium heparin tube (BD, Franklin Lakes, NJ) collected during the first follow up visit, 2 weeks after commencement of twice daily topical treatment of a 1.5% cream formulation. A pre-dose trough sample will be collected just prior to application of the treatment on the day of their follow-up visit. After application in clinic, blood samples will be collected at 1hr, 2hr, and 4hr to understand the rate and extent of systemic exposure. Bioanalytical measurements will be

**Abbreviated Title:** Topical ruxolitinib in cGVHD

**Version Date:** 01/25/2021

conducted on an ultra HPLC-MSMS system using an assay developed and validated by the Blood Processing Core.

This data will be used to monitor ruxolitinib plasma concentrations in order to primarily understand the rate and extent of systemic exposure of ruxolitinib from a 1.5% strength topical cream applied to skin affected with epidermal cGVHD. Secondarily, these plasma measurements can also be used to correlate to pharmacodynamic endpoints, clinical response, and toxicity.

The samples will be placed immediately on wet ice and refrigerated. The date and exact time of each blood draw should be recorded on the sample tube and the PK sheet.

Please e-mail [REDACTED] at least 24 hours before transporting samples (the Friday before is preferred).

For sample pickup, [REDACTED].

For immediate help, [REDACTED]).

For questions regarding sample processing, contact [REDACTED]. Upon arrival in the Blood Processing Core (BPC), samples will be centrifuged and the plasma transferred into cryovials for storage at -80°C until the time of analysis. In addition, samples will be barcoded as described in Section 5.2.2.

